4.5.3. Laboratory Safety Variables

Hematology, chemistry, urinalysis, and the coagulation panel will be analyzed by local laboratory. Plasma for PT and aPTT biomarkers will be analyzed by a central laboratory. Detailed instructions for blood sample collection are in the laboratory manual provided to study sites.

Samples for laboratory testing will be collected at visits according to [Table 4](#). Tests (Blood Chemistry, Hematology, Urinalysis, and Other Laboratory Tests) are described in protocol Section 9.2.3.7.

4.5.4. Vital Signs

The following vital signs parameters will be collected at each clinic visit from screening to end of study (EOS) or at the time of early termination (ET):

- Temperature (°C)
- Semi-recumbent blood pressure (mmHg)
- Pulse rate (beats/min)
- Respiratory rate (breaths/min)

4.5.5. ECG

A standard 12-Lead ECG will be performed at time points according to [Table 3](#). Heart rate will be recorded from the ventricular rate and the PR, QRS, and QT (QTcB and QTcF) intervals will be recorded. The ECG strips or reports will be retained with the source.

4.6. Pharmacokinetic Variables

The Pharmacokinetic (PK) variable is the concentration of total REGN9933 in serum at scheduled time points on [Table 3](#) and [Table 4](#).

4.6.1. Drug Target Variables

The drug target variable is the concentration of total FXI in plasma at each time point. These sampling timepoints are specified in [Table 3](#) and [Table 4](#).

4.7. Immunogenicity Variables

The immunogenicity variables are ADA status, titer, and time-point/visit. Samples in this study will be collected at the clinical visits as specified in [Table 3](#) and [Table 4](#).

4.8. Pharmacodynamic and Other Biomarker Variables

Plasma for aPTT and PT biomarkers will be analyzed by a central laboratory, and they will be used for the secondary PD endpoints.

Additional PD and biomarker variables include FXI:C (a measure of FXI activity), intrinsic-pathway-triggered thrombin generation, and extrinsic-pathway-triggered thrombin generation. Samples in this study will be collected at the clinic visits specified in [Table 3](#) and [Table 4](#).

5. STATISTICAL METHODS

Unless otherwise stated, the following conventions will be applied when presenting summary level statistics for data.

Continuous variables will be summarized within each treatment group, presenting the following descriptive statistics: the number of participants reflected in the calculation (n), average, sample standard deviation (SD), median, minimum, maximum, 1st quartile and 3rd quartile.

Categorical or ordinal data will be summarized within each treatment group by frequency (i.e. total number of observations within each level of the categorical variable in a given treatment group) and percentages. All levels of the categorical variable will be included. If there are observations where the level of the categorical variable is missing, a separate category titled “Missing” will be created. For categorical variables that are ordinal in nature, the order in which the levels of the categories are displayed will be consistent with the natural ordering of the category levels. Percentages will also be calculated for each level of the categorical variables with respect to the total sample size for the respective treatment arm.

5.1. Demographics and Baseline Characteristics

Demographic and baseline characteristics will be summarized descriptively by treatment group based on SAF.

5.2. Medical History

Medical history will be coded using the Medical Dictionary for Regulatory Activities (MedDRA®). The frequency and percentage of each medical history will be summarized by associated primary SOC and PT for each treatment arm on the SAF. The table will be sorted by decreasing frequency of SOC followed by PT based on the overall incidence across treatment groups.

5.3. Prior / Concomitant Medications

The prior and concomitant medication will be descriptively summarized by treatment group on the SAF, sorted by decreasing frequency of ATC Level 2 and ATC level 4 of the total group. The use of anti platelets, anticoagulants (outside of assigned treatments), and NSAIDs may be included if deemed necessary.

5.4. Subject Disposition

The following summaries of number and percentage by each treatment group and overall group will be provided:

- The number of participants screened (signed the informed consent form) and the reasons for screen failure
- The number of participants randomized (received a randomization number)
- The number of participants treated

- The total number of participants who discontinued the study treatment and the reasons for the discontinuation
- A cross-tabulation of participants by planned and actual randomization strata for quantifying the mis-stratification

5.5. Measurement of Treatment Compliance

Treatment compliance will be summarized by treatment group.

For each study arm, its compliance will be calculated as follows:

$$\text{compliance \%} = 100\% \times \frac{\text{number of actual administrations}}{\text{number of planned administrations}}$$

where the number of planned administrations by each study drug is calculated as:

- For participants assigned to the enoxaparin arm, the number of planned administrations is the number of days in the on-treatment period, which is defined as the period from the date of the first dose of study drug to the time of venography (or day 12, whichever is earlier).
- For participants assigned to the apixaban arm, the number of planned administrations is two times of the number of days in the on-treatment period, which is defined as the period from the date of the first dose of study drug to the time of venography (or day 12, whichever is earlier).
- For participants assigned to the REGN9933 arm, the number of planned administrations is one.

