8. STUDY TREATMENTS

8.1. Investigational and Reference Treatments

Study interventions are presented in [Table 1](#).

Treatment arms are:

- REGN9933 300 mg IV, single dose administered as 0.5-hour infusion
- Enoxaparin 40 mg SC, daily through the time of venography (or day 12, whichever is earlier)
- Apixaban 2.5 mg PO, BID through the time of venography (or day 12, whichever is earlier)

For REGN9933, a single IV dose will be administered 12 to 24 hours after surgery (>12 hours after removal of the spinal/epidural anesthesia needle/catheter).

For enoxaparin, dosing will begin 12 to 24 hours after surgery (>12 hours after removal of the spinal/epidural anesthesia needle/catheter). Dosing will continue through the time of venography (or day 12, whichever is earlier). If a participant is discharged from the hospital prior to the venogram, the participant may choose to self-administer enoxaparin or have a designated person administer enoxaparin at home. Injection training of enoxaparin will be provided. After training, observation of self-administration/designated person will be conducted by clinical site personnel. Once this observation is considered satisfactory, then the study drug can be subsequently administered independently by the participant/designated person for the remainder of the dosing period.

For apixaban, dosing will begin 12 to 24 hours after surgery (>12 hours after removal of the spinal/epidural anesthesia needle/catheter). Dosing will continue through the time of venography (or day 12, whichever is earlier). Apixaban dosing will continue at home if a participant is discharged from the hospital prior to the venogram.

A patient diary will be provided to record compliance of at-home dosing of enoxaparin/apixaban. The diary should be completed upon each study drug administration.

Instructions on dose preparation are provided in the pharmacy manual.

Table 1: Study Interventions Administered

Intervention Name	REGN9933	Enoxaparin	Apixaban
Intervention Description	300 mg IV, single dose administered as 0.5-hour infusion	40 mg SC, daily through the time of venography	2.5 mg PO, BID through the time of venography
Type	Biologic	Drug	Drug
Dose Formulation	Lyophilized Powder	Pre-filled Syringe-Liquid Solution	Film Coated Tablet
Unit Dose Strength(s)	265 mg in 20 mL vial	40 mg, 0.4 mL, pre-filled syringe	2.5 mg tablets, in a blister pack/wallet carton

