9. STUDY SCHEDULE OF EVENTS AND PROCEDURES

9.1. Schedule of Events

In light of the public health emergency related to COVID-19, the continuity of clinical study conduct, and oversight may require implementation of temporary or alternative mechanisms. Examples of such mechanisms may include, but are not limited to, any of the following: phone contact, virtual visits, telemedicine visits, online meetings, non-invasive remote monitoring devices, use of local clinic or laboratory locations, and home visits by skilled staff. Additionally, no waivers to deviate from protocol enrollment criteria due to COVID-19 will be granted. All temporary mechanisms utilized, and deviations from planned study procedures are to be documented as being related to COVID-19 and will remain in effect only for the duration of the public health emergency.

Study assessments and procedures are presented by study period and visit in [Table 2](#).

Definitions

For safety variables, 3 observation periods are defined:

- Screening period - the time from signing the ICF to before the first dose of study drug.
- On-treatment period - the day from first dose of study drug to the date of day 12.
- Follow-up period - the end of the on-treatment period to EOS visit.

Table 2: Schedule of Events

Study Procedure	Screening	On-treatment			Follow-up	
	Visit 1	Baseline Visit 2	Visit ^{1,2} 3	Visit ¹ 4	Visit 5	End of Study/ Visit 6
Day	-30 to -1	1	5	10	30	75
Window (day)			±1	±2	±3	±5
Screening/Baseline:						
Inclusion/Exclusion	X					
Informed consent	X					
Informed consent for pharmacogenomics research (optional)	X					
Informed consent for future biomedical research (optional)	X					
Medical History	X					
Demographics	X					
FSH ³	X					
GFR (MDRD)	X					
Urine drug screen	X					
Randomization		X ⁴				
Treatment:						
TKA		X				
Administer REGN9933		X ⁵				
Administer enoxaparin			X ⁶			
Administer apixaban			X ⁶			
Patient diary (for self-administration of apixaban/enoxaparin)			X			
Efficacy:						
Venography of the operated leg				X		
Assessment for symptomatic VTE ⁷		X	X	X	X	X
Safety:						
Height	X					
Weight	X					

Study Procedure	Screening	On-treatment			Follow-up	
	Visit 1	Baseline Visit 2	Visit ^{1,2} 3	Visit ¹ 4	Visit 5	End of Study/ Visit 6
Vital Signs	X	X	X	X	X	X
Physical examination	X	X				X
Electrocardiogram	X					
Assessment for surgical site bleeding		X	X	X		
Assessment for bleeding events		X	X	X	X	X
Adverse events	X	X	X	X	X	X

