11.4.5.1. Adverse Events

Definitions

For safety variables, the 3 observation periods are defined in Section 9.1. Treatment-emergent adverse events are defined as those that are not present at baseline or represent the exacerbation of a pre-existing condition after the dose administrations.

Analysis

Summaries of all TEAEs by treatment group will include:

- The number (n) and percentage (%) of participants with at least 1 TEAE by SOC and PT
- TEAEs by severity (according to the grading scale outlined in Section 10.2.5), presented by SOC and PT
- Treatment-emergent AESIs
- Treatment-emergent adverse events leading to permanent treatment discontinuation will be summarized by treatment group.

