11.4.5.4. Treatment Compliance

The compliance with study treatment will be calculated as follows:

$$\text{compliance \%} = 100\% \times \frac{\text{number of actual administrations}}{\text{number of planned administrations}}$$

The number of planned administrations will be calculated as:

- For participants assigned to the enoxaparin arm, the number of planned administrations is the number of days in the on-treatment period
- For participants assigned to the apixaban arm, the number of planned administrations is two times of the number of days in the on-treatment period
- For participants assigned to the REGN9933 arm, the number of planned administrations is one

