1.4. Modifications from the Statistical Section in the Final Protocol

There is no modification from the statistical section in the final protocol.

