2. INVESTIGATION PLAN

2.1. Study Design

The study consists of the following periods: a screening period (day -30 to day -1) and a 75-day open-label treatment and follow-up period with REGN9933 or enoxaparin or apixaban.

Participants who are at least 50 years of age and undergoing elective, unilateral TKA will be randomized after surgery to one of 3 treatment arms—REGN9933, enoxaparin, apixaban—in a ratio of 1:1:1, in a parallel manner. Randomization will be stratified based on study site and age (<70 vs \geq 70 years of age). Approximately 120 participants will be enrolled in each arm, for a total of up to approximately 360 participants in the study.

After providing informed consent, participants will undergo screening, which can occur from approximately day -30 to -1 (day 1 is defined as the day of TKA surgery). Participants will be randomized after completion of surgery to treatment in one of the following groups:

[figure not shown]
- REGN9933 300 mg IV, once
- Enoxaparin 40 mg subcutaneous (SC), daily through the time of venography or day 12, whichever is earlier
- Apixaban 2.5 mg orally (PO), BID, daily through the time of venography or day 12, whichever is earlier

Dosing with REGN9933 will occur 12 to 24 hours after the end of surgery.

Dosing with enoxaparin or apixaban will begin 12 to 24 hours after the end of surgery and will continue through the day of venography (or day 12, whichever is earlier). Administration of enoxaparin prior to TKA surgery is not permitted in this study (see protocol Section 7.2.2 Exclusion criterion 10 and Section 8.8.1). All investigators must comply and satisfy all requirements for the local risk management plan or equivalent for apixaban and enoxaparin where applicable and before dosing participants.

Below is the study flow diagram depicting the different periods of the study with the scheduled visits and treatment administrations.

Figure 1: Study Flow Diagram

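### SAP 5.5 plans two apixaban doses for every day from first dose to venography, with no rule for partial first and last days or for counting days, so a fully adherent participant need not score 100%

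*SAP*

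**What the plan says.** Both documents define compliance as actual administrations divided by planned administrations, times 100%. In SAP 5.5 planned administrations are one for REGN9933, one per day for enoxaparin and, for apixaban, "the number of planned administrations is two times of the number of days in the on-treatment period". The SAP defines that period as "the period from the date of the first dose of study drug to the time of venography", with day 12 as the limit.

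Protocol 11.4.5.4 uses the same multipliers: "For participants assigned to the enoxaparin arm, the number of planned administrations is the number of days in the on-treatment period", and twice that for apixaban. It does not define the period. The only protocol definition is in 9.1, where the on-treatment period is "the day from first dose of study drug to the date of day 12". That definition is introduced for safety variables, and the adverse event section refers back to it: "For safety variables, the 3 observation periods are defined in Section 9.1". SAP 1.4 states: "There is no modification from the statistical section in the final protocol".

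On dosing, the comparators start between 12 and 24 hours after the operation ends (Protocol 6.1 and 8.1), and day 1 is the day of surgery. The stop is worded in two ways. Protocol 8.1 and the SAP 2.1 arm list use the time of venography (in the SAP, "daily through the time of venography or day 12, whichever is earlier"). Protocol 6.1 and 8.8.2 and the dosing paragraph of SAP 2.1 use the day of venography. Neither document says which wording governs compliance.

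**The concern.** The period starts at a date, ends at a clock time, and is then counted in whole days and doubled. Both ends can be partial for a twice-daily drug. If the first tablet is an evening tablet, two doses are planned on that date and one is possible. If dosing stops when the venogram is done, one or both of that date's tablets are planned but not due. Enoxaparin is exposed only at the far end, when the venogram precedes that day's injection. A completed REGN9933 infusion scores 1/1.

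Any error therefore falls on the comparators, and mostly on apixaban, which Protocol 3.2.1 uses as calibrator and positive control. If the expected difference between apixaban and enoxaparin does not appear, readers will look at apixaban compliance. In an open-label trial with home dosing, a shortfall created by the definition could be taken for missed tablets.

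**Working it through.** The documents give no compliance figure to reproduce, so the check is an enumeration for a participant who takes every dose that is due.

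**Inputs.** Venogram on day v, within days 8-12, target day 10 (Protocol 9.2.2.1). The first dose can fall in the evening of day 1 (operation ended before noon), the morning of day 2, or the evening of day 2 (operation ended in the evening). Clock times are assumptions; only the order of tablet and venogram matters. The day-count convention is also an assumption, so both conventions are shown.

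**A. Both end dates counted.** Days n = v − first-dose day + 1; planned = 2n. For v = 10:

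| First dose | Planned | Day stop | Time stop, venogram between tablets | Time stop, venogram before morning tablet |
|---|---|---|---|---|
| Morning, day 2 | 2 × 9 = 18 | 18/18 = 100% | 17/18 = 94.4% | 16/18 = 88.9% |
| Evening, day 1 | 2 × 10 = 20 | 19/20 = 95.0% | 18/20 = 90.0% | 17/20 = 85.0% |
| Evening, day 2 | 2 × 9 = 18 | 17/18 = 94.4% | 16/18 = 88.9% | 15/18 = 83.3% |

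If the venogram follows the evening tablet, the time stop gives the day-stop column. The ranges are thus 94.4-100% (day stop) and 83.3-100% (time stop). After an evening first dose 100% is out of reach; the best case over the window is 23/24 = 95.8% (v = 12). The lowest score over the window is 11/14 = 78.6% (v = 8).

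The 83.3% needs three things together: a single tablet on day 2, the time stop, and a venogram before the morning tablet. With strict 12-hourly dosing, operations ending 09:00-18:00 and venograms at 08:00-17:00 (assumed hours), the day-10 range is 85-100% for the time stop and 94-100% for the day stop.

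**B. Elapsed days.** Days = v − first-dose day. For v = 10:

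- Morning, day 2 (planned 16): 18/16 = 112.5%, 17/16 = 106.25%, 16/16 = 100%.
- Evening, day 1 (planned 18): 19/18 = 105.6%, 18/18 = 100%, 17/18 = 94.4%.
- Evening, day 2 (planned 16): 17/16 = 106.25%, 16/16 = 100%, 15/16 = 93.75%.

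The range is about 94-112.5%.

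**C. Enoxaparin, first dose day 2, v = 10.** Both end dates counted: 9/9 = 100%, or 8/9 = 88.9% if the time stop precedes that day's injection. Elapsed days, with the venography-date injection given: 9/8 = 112.5%. Counting both end dates is therefore the more natural reading, but the SAP does not state it.

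**D. Protocol 9.1 period, for comparison.** Running to day 12, the same adherent enoxaparin participant would score 9/11 = 81.8%, and the best apixaban case 18/22 = 81.8%. Ending the period at venography, as SAP 5.5 does, is an improvement.

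**The case against.** The strongest reply is that the shortfall depends on a counting rule nobody wrote down. On elapsed days, an evening first dose on day 1 with a day-10 venogram scores 18/18 = 100% under the time stop (venogram between tablets) and 19/18 = 105.6% under the day stop, so it is not true in general that such a participant falls short. This stands, and it means the 83-100% range must be stated as conditional. It does not rescue the formula, which then reports more than 100% for others.

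Second, Protocol 8.8.2 describes completed treatment as running through the day of venography, and 6.1 agrees. On that reading, with both end dates counted, an adherent apixaban participant is short by at most one dose and enoxaparin is unaffected. This also stands, but the one-dose first date remains: 19/20 = 95.0%.

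Third, a reader might infer that SAP 5.5 replaced a day-12 denominator set by the protocol and that SAP 1.4 is therefore false. The documents do not support that firmly. The 9.1 period is defined for safety variables and lies outside the statistical section, which is all that SAP 1.4 speaks to. Protocol 11.3.2 lists treatment compliance separately from the clinical safety variables, and 11.4.5.4 leaves the period undefined. SAP 5.5 can fairly be read as supplying the missing definition. What remains is one term with two meanings, which merits a note.

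Fourth, the consequences are small. SAP 5.6 reports days on which comparator was received, SAP 5.4 reports discontinuations, and no efficacy analysis uses compliance. This is accepted and sets the severity.

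**Conclusion.** The point holds, with minor severity. SAP 5.5 gives a stated rule that misreports some fully adherent apixaban participants under either way of counting days. The least contestable example is an evening first dose on day 1 and a day-10 venogram under the day stop: 95.0% with both end dates counted, 105.6% with elapsed days.

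It would go too far to say that the SAP systematically understates apixaban compliance, or that 83% is a typical score. The direction depends on an unstated convention and the low end is an edge case. Nor is there a case that the primary result or any analysis set is affected. The figures assume that every due dose was taken and that the first dose falls at one of the three times considered; they do not predict how often each case will arise.

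**What to change.** Change SAP 5.5 only, identically for all comparator participants:

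> Days are calendar dates from the date of first dose, inclusive, through the day before venography, or through day 12 if no venogram has been done by then. Planned administrations are one per date for enoxaparin and two per date for apixaban, but one on the first date if the first apixaban dose was the evening dose. Actual administrations are counted over the same dates.

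Check at v = 10 for apixaban: morning day 2, 2 × 8 = 16, so 16/16; evening day 1, 2 × 9 − 1 = 17, so 17/17; evening day 2, 2 × 8 − 1 = 15, so 15/15. Enoxaparin from day 2 gives 8/8. All are 100%, whichever stop wording a site followed.

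Optionally, add a line to SAP 1.4 that 5.5 uses its own on-treatment period for compliance, different from the safety period in Protocol 9.1.

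The cost is one paragraph and one derivation. It needs dose dates, which the dose records and diary give, and whether the first apixaban dose was a morning or evening one. I assume the first-dose time is recorded, since the 12 to 24 hour window cannot be checked without it. No venogram clock time is needed. The downside is that doses on the venography date are not assessed. Participants whose venogram is cancelled after a confirmed event are still counted to day 12, as SAP 5.5 now implies.

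No protocol dosing text needs to change. Rewriting the stop in Protocol 8.1 would call for an approved amendment (Protocol 14) and is unnecessary here. SAP section 1 allows revision before database lock if the change is documented.

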5.6. Treatment Exposure

The duration of exposure during the treatment period will be presented by treatment group and calculated as:

- For participants assigned to the enoxaparin or apixaban arm, exposure will be summarized by the number of days that the participant received enoxaparin or apixaban administrations.

5.7. Analysis of Efficacy Variables

The efficacy analyses will be performed using the mITT analysis set.

Pooling of Sites/Centers

For this multi-center study, a small number of participants are anticipated at some sites. Since these study sites may not provide appropriate information to allow the analysis, the efficacy analyses adjusted/stratified by country instead of site will be conducted.

